2.6.3 Exploratory efficacy endpoints

The exploratory efficacy endpoints include:

- A weekly CSBM rate increase of 1 or more compared to baseline and an absolute rate of 3 or more CSBMs per week in the Fixed Dose period (i.e., this is a modification of the Prokinetic Response secondary endpoint using “AND” instead of “OR” as the criterion).
- A weekly SBM rate increase of 1 or more compared to baseline and an absolute rate of 3 or more CSBMs per week in the Fixed Dose period.
- Change from baseline in the weekly CSBM rate during the Placebo Withdrawal and Washout periods.
- Change from baseline in the weekly SBM rate during the Placebo Withdrawal and Washout periods.
- Change from baseline in stool ease of passage during the Placebo Withdrawal and Washout periods.
- Change from baseline in stool consistency during the Placebo Withdrawal and Washout periods.
- Change from baseline in suppository/enema use during Placebo Withdrawal and Washout periods.
- Improvement in frequency and/or severity of hallucinations/delusions during the Fixed Dose period over baseline: Improvement is defined as an improvement of 2.33 points or greater reduction in score from baseline on the Scale for the Assessment of Positive Symptoms -Parkinson's Disease (SAPS-PD). Up to 40% of subjects are expected to have minor or major hallucinations and/or delusions. The SAPS-PD will be administered at Screening, and subsequently will only be administered to those subjects with hallucinations and/or delusions (as determined by an SAPS-PD score >0 at the Screening visit).
- Improvement of the symptoms of Parkinson's Disease as assessed by the UPDRS: The standard four-part UPDRS will be administered to determine whether there is any deterioration in overall scores during the treatment period. Motor deterioration will be assessed from Part 3 of the UPDRS, but total score will also be reported. ***The assessment will be performed during the “ON” phase, approximately 60 minutes after taking levodopa.***
- Improvement in mood as assessed by the Beck Depression Index (BDI-II): The 21-item BDI-II assesses the intensity of depression. Each item is a list of four statements arranged in increasing severity about a particular symptom of depression.

- Improvement in cognition as assessed by the MMSE: The MMSE is an 11-item examination with a score ranging from 0 – 30 with a higher score indicating better memory. The MMSE will be summarized over time.
- Improvement in sleep as assessed by sleep diaries.
- Change in plasma L-Dopa levels 20, 40, and 60 minutes after L-Dopa and ENT-01 dose: An increase of >30% in peak plasma level during treatment versus baseline would indicate clinically significant increase in absorption attributable to ENT-01 (10 subjects only).
- Change in stool microbiome during treatment: Since ENT-01 has antimicrobial properties in vitro, it may alter the intestinal microbiome; the subject's stool will be analyzed for common intestinal bacteria and viruses at Baseline, Fixed Dose, and Washout periods (10 subjects only).

2.6.4 Pharmacokinetic (PK) Endpoints

PK samples for levodopa will be collected from trial patients according to the instructions detailed in the lab manual and in accordance with the protocol schedule. A separate SAP will be prepared for the PK analysis.

2.6.5 Safety Endpoints

Safety assessments performed during the study include:

- Adverse Events collection and reporting
- Physical Examinations
- Vital sign assessment
- Laboratory assessment including Hematology, Serum chemistry, and Urinalysis
- Electrocardiogram (ECG).
- The Columbia Suicide Severity Rating Scale (C-SSRS)

AEs will be coded according to the latest version of the Medical Dictionary for Regulatory Activities (MedDRA). The intensity/severity of AEs will be graded according to NCI-CTCAE (Common Terminology Criteria for Adverse Events.).

A treatment-emergent adverse event (TEAE) is defined as any event not present prior to the initiation of the treatments or any event already present that worsens in either intensity or frequency following exposure to the treatments.

The C-SSRS is a questionnaire used to measure of suicidal ideation and behavior.

2.6.6 Tolerability Endpoints

The tolerability endpoint is referred to as the dose limiting toxicity (DLT). These adverse events are considered as DLT:

- Recurrent vomiting defined as 3-5 episodes of vomiting within 24 hours of taking study medication/placebo

- Recurrent diarrhea defined as 4 or more episodes of diarrhea within 24 hours of taking study medication/placebo
- Abdominal pain defined as moderate pain that limits instrumental activities of daily living (ADL) (e.g., preparing meals, shopping for groceries or clothes, using the telephone, managing money, etc.) within 24 hours of taking study medication/placebo
- Dizziness defined as lightheadedness or fainting on rising from lying to sitting or standing that limits instrumental ADL and severe enough to indicate non-urgent medical intervention within 24 hours of taking study medication/placebo.

It is anticipated that all subjects receiving active treatment will exhibit a prokinetic effect at a dose lower than DLT and less than or equal to 250 mg. Subjects reaching DLT before a prokinetic effect will be treated at the highest dose at which they did not experience a DLT.

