3 OBJECTIVES AND ENDPOINTS

3.1 Primary Objective and Endpoints

The purpose of this study is to evaluate the safety, tolerability, and efficacy of repeated oral doses of ENT-01 for up to 25 days in subjects with Parkinson's Disease-related constipation in a randomized, double-blind, placebo-controlled study.

Safety:

The **primary safety objective** of this study will be the evaluation of the safety of repeated daily oral dose of ENT-01 for up to 25 days in subjects with PD-related constipation.

Safety endpoints will include adverse events as evaluated with subject self-reporting, vital signs, clinical chemistry and hematology blood analyses, urinalysis, and electrocardiogram (ECG).

It is anticipated that no more than 2 subjects out of 60 (3.3%) will have an adverse event of grade 4 or 5 that is at least possibly related to ENT-01 in this Study. Should there be more than 2 subjects with an adverse event grade 4 or 5 that is at least possibly related to ENT-01 in the cohort of subjects randomized to ENT-01, the study will be put on an immediate clinical hold.

In addition, individual safety stopping rules will include:

- Reaching dose-limiting tolerability (DLT) before a prokinetic effect
- Having a non-DLT gastrointestinal adverse event > grade 3 within 24 hours of taking study medication or placebo, that is at least possibly attributable to ENT-01
- A fall in systolic blood pressure to < 80 mm Hg upon rising from lying to sitting or standing
- A fall in diastolic blood pressure to < 40 mm Hg upon rising from lying to sitting or standing
- Elevation of liver function tests (LFTs) > 3 times the upper limit of normal(ULN)

Tolerability

The primary tolerability objectives will be evaluation of recurrent vomiting, recurrent diarrhea, abdominal pain and dizziness.

Tolerability endpoints are referred to as the DLT and will include:

- Recurrent vomiting defined as 3-5 episodes of vomiting within 24 hours of taking study medication/placebo
- Recurrent diarrhea defined as 7 or more episodes of diarrhea within 24 hours of taking study medication/placebo
- Abdominal pain defined as moderate pain that limits instrumental activities of daily living (ADL) (e.g., preparing meals, shopping for groceries or clothes, using the telephone, managing money, etc.) within 24 hours of taking study medication /

placebo.

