- Reaches the maximum dose of 10 tablets (i.e., 250 mg for active treatment); or,
- Reaches the dose limiting tolerability(DLT).

If the subject has 4 or more episodes of diarrhea with a consistency of 6-7 (see [APPENDIX 6](#)) within 24 hours of a dose on 2 consecutive days at a given dose, the dose will be reduced by 25 mg and fixed at that dose assuming diarrhea subsides.

Should a prokinetic response not occur at 250 mg (or 10 tablets), subjects will continue to take 10 tablets daily for the remainder of the 25-day treatment period.

During this visit, the following assessments and procedures will be performed:

- Review of Inclusion/Exclusion Criteria
- Confirmation of eligibility: To be randomized to receive double-blind study medication in this study, subjects must meet the following criteria:
 - Have at least 11 ‘Available Data Days’ (days with e-Diary compliance sufficient for determining whether a CSBM occurred) (Subjects with fewer than 11 diary days will continue to fill in their diaries until 11 days’ worth of information is available and randomization will be delayed). Have had fewer than 3 complete spontaneous bowel movements per week based upon the average CSBM rate reported during the 2-week Screening Period. This rate will be calculated centrally with a computer-based system and requested by the site the day before randomization.
 - Be deemed eligible for randomization by the enrollment committee
 - Weight
 - Orthostatic Vital Signs
 - 12-lead ECG

- Pregnancy Testing – For women of child-bearing potential only.
- Randomization: Sites will utilize a centralized, computer-based system (IWRS) to obtain the randomization bottle (s) assigned to each subject.
- In-clinic Levodopa Dosing – Subjects will take their morning dose of levodopa in the clinic.
- Subjects will be given study medication and will take their first dose the following day at home, on an empty stomach. The day after Visit 2 will be the first day of treatment.
- Levodopa PK Draws – The first daily dose of L-Dopa will be administered in clinic. Blood samples will be obtained pre-L-Dopa dose and at 20, 40-and 60-minutes post-dose. (Applicable to the levodopa PK sub-study only.)
- Dispense Rescue Medication, as needed. Subjects continue appropriate use of rescue medication, ensuring adequate bowel movements every 3 days.
- AE Review
- Prior and Concomitant Meds
- C-SSRS

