8.2 NCI CTC AEv4.03 Definitions of Dose Limiting Adverse Events

Adverse Event	Grade 1	Grade 2	Grade 3	Grade 4	Grade 5
Diarrhea (watery stool)	Increase of <4 stools a day over baseline	Increase of 4 - 6 stools per day over baseline; moderate increase in ostomy output compared to baseline	Increase of ≥ 7 stools per day over baseline; incontinence; hospitalization indicated; severe increase in ostomy output compared to baseline; limiting self-care ADL	Life threatening complications ; urgent intervention indicated	Death
Vomiting	1-2 distinct episodes per 24 hrs	3-5 distinct episodes per 24 hrs	6 or more distinct episodes in 24 hrs; tube feeding, TPN or hospitalization indicated	Life-threatening consequences ; urgent intervention indicated	Death
Abdominal pain	Mild pain	Moderate pain; limiting instrumental ¹ ADL	Severe pain; limiting self-care ADL ²	-	-
Postural hypotension ³	Mild, transient lightheadedness or dizziness upon rising from	Moderate lightheadedness , dizziness or fainting upon	Severe lightheadedness, dizziness or fainting upon rising from	Life-threatening and urgent intervention indicated	Death

	lying or sitting position that does not interfere with ADL	rising from lying or sitting position that limits instrumental ADL; Non-urgent medical intervention indicated	lying or sitting position that limits self-care ADL; Medical intervention or hospitalization indicated		
--	--	---	--	--	--

¹Preparing meals, shopping for groceries or clothes, using the telephone, managing money, etc.

²Bathing, dressing and undressing, feeding self, using the toilet, taking medications, and not bedridden

³Definition adapted from combining CTCAE definitions for Hypotension and Dizziness

8.3 Criteria for Dose Limiting Toxicity (DLT) Endpoints:

Recurrent vomiting: 3-5 episodes of vomiting within 24 hours of taking study medication/placebo (Grade 2 adverse event)

Recurrent diarrhea: >7 episodes of diarrhea within 24 hours of taking study medication/placebo (Grade 3 adverse event)

Abdominal pain: Moderate pain that limits instrumental activities of daily living within 24 hours of taking study medication/placebo (Grade 2 adverse event)

Dizziness: Moderate lightheadedness or fainting upon rising from lying to sitting or standing and severe enough to require medical intervention within 24 hours of taking study medication/placebo (Grade 2 adverse event) or either a systolic blood pressure less than 80mmHg or diastolic blood pressure less than 40mm Hg.

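### The SAP counts 4 or more diarrhoea episodes as dose limiting, Protocol version 7 requires 7 or more, and the SAP declares no change

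*SAP*

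**What the plan says.** The protocol synopsis and Protocol 3.1 list recurrent vomiting, recurrent diarrhoea, abdominal pain and dizziness as the primary tolerability endpoints. SAP 1.2.1 repeats them as the primary tolerability objective. Three current sections define the diarrhoea item:

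- SAP 2.6.6: "Recurrent diarrhea defined as 4 or more episodes of diarrhea within 24 hours of taking study medication/placebo"
- Protocol 3.1: "Recurrent diarrhea defined as 7 or more episodes of diarrhea within 24 hours of taking study medication/placebo"
- Protocol 8.3: ">7 episodes of diarrhea within 24 hours of taking study medication/placebo (Grade 3 adverse event"

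The CTCAE table in Protocol 8.2 gives Grade 3 diarrhoea as "Increase of ≥ 7 stools per day over baseline; incontinence" (with further criteria) and Grade 2 as "Increase of 4 - 6 stools per day over baseline" (likewise).

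Protocol 4.2 has a separate rule that uses the number 4, as an instruction to lower the dose: "If the subject has 4 or more episodes of diarrhea with a consistency of 6-7" and, after a reference to the Bristol chart, "within 24 hours of a dose on 2 consecutive days at a given dose, the dose will be reduced by 25 mg". Protocol 4.2 lists reaching DLT separately, as one of the events that end escalation.

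Protocol 9.2.3 and SAP 4.8.10 summarise the frequency of each DLT endpoint by treatment group and dose level. SAP section 5 states that nothing differs between the protocol-defined analyses and the SAP.

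**The concern.** A primary endpoint needs one definition, and here the answer depends on which document the programmer opens. The SAP cut-off takes in a band of milder events, roughly Grade 2 in the protocol's own table, that version 7 does not treat as dose limiting. If the SAP is followed, the report will call some events dose limiting although, under version 7, they would not have ended escalation as DLTs. A reader could not then reconcile the DLT counts with the dosing rules.

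Timing adds to this. Protocol 9.2.6 records that the first cohort has already been analysed unblinded, and SAP 4.3 foresees a further unblinded analysis. A threshold left open now could later be settled with results in view, or appear to have been.

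**Working it through.** No figure in the plan depends on the DLT threshold, so there is nothing to reproduce. The check is to apply each rule to the same subject.

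| Worst 24 hours after a dose | SAP 2.6.6 | Protocol 3.1 | Protocol 8.3, read literally | Protocol 4.2 dose reduction |
|---|---|---|---|---|
| 0 to 3 episodes | no DLT | no DLT | no DLT | no |
| 4 to 6, on one day only | **DLT** | no DLT | no DLT | no |
| 4 to 6, on two consecutive days at one dose, Bristol type 6-7 | **DLT** | no DLT | no DLT | yes, 25 mg |
| exactly 7 | DLT | DLT | no DLT | only if two consecutive days qualify |
| 8 or more | DLT | DLT | DLT | only if two consecutive days qualify |

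**Step 1, SAP against Protocol 3.1.** Subjects counted by the SAP but not by Protocol 3.1 = (worst count 4 or more) − (worst count 7 or more) = subjects whose worst count is 4, 5 or 6.

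**Step 2, Protocol 3.1 against Protocol 8.3.** The difference is (7 or more) − (8 or more) = subjects whose worst count is exactly 7. The Grade 3 label in 8.3, read with the table in 8.2, points to 7 or more. This is a slip at one value and secondary to step 1.

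**Step 3, could the SAP be restating Protocol 4.2?** No. The 4.2 rule needs Bristol type 6-7 stools on two consecutive days, and its consequence is a lower dose. SAP 2.6.6 needs neither condition. A single day with 4 to 6 episodes has no status under version 7 but is a DLT in the SAP.

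**Step 4, severity.** The match between 4 to 6 episodes and Grade 2 is approximate, because the CTCAE grade counts the increase over baseline whereas the DLT definitions count episodes.

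**Step 5, size.** The number of subjects in the 4-to-6 band is not in the documents. As a scale only: with about 40 ENT-01 subjects planned in the 1:1 cohort, each reclassified subject moves the diarrhoea DLT frequency in that arm by 1/40 = 2.5 percentage points. It moves more at a dose level that fewer subjects reached.

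**The case against.** Four arguments can be made for leaving the SAP as it is.

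**The SAP may simply be out of date.** It has screening at Day -14 where version 7 has Day -21, narrower visit windows, sleep endpoints, 10-subject sub-studies where the protocol has 20, and different appendix numbers. Its no-change statement is also qualified as of its date. This is a fair reading. A reader might infer that the sponsor lowered the threshold on purpose, and the documents do not show that. An outdated definition still gives the wrong table if it is programmed.

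**A threshold of 4 is clinically defensible and counts more events, not fewer.** The vomiting DLT sits at Grade 2 ("3-5 distinct episodes per 24 hrs"), so placing diarrhoea near Grade 2 would be coherent, and a higher count is conservative for safety. It would also be awkward to lower the reported count after the first cohort was unblinded. This stands as a reason to show both counts. It does not make 4 the protocol's definition, since Protocol 8.3 explicitly labels the diarrhoea DLT Grade 3.

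**Nothing inferential depends on it.** This is correct. SAP 4.8 plans no hypothesis test on safety data, and the DLT table is descriptive.

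**The DLT table covers only the Dose Adjustment period, which might look like a further fault.** The documents do not support calling it one. Protocol 9.2.3 and SAP 4.8.10 agree on the period, and SAP 4.8.2 tabulates adverse events by grade, dose and period, including the Fixed Dose period.

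**Conclusion.** The mismatch is certain: it lies in current text of both documents, on a primary tolerability endpoint, and SAP section 5 does not disclose it. It affects one row of a descriptive table, by exactly the subjects whose worst 24 hours had 4 to 6 episodes. It should be corrected, but it does not threaten the efficacy conclusion, the error rate or the power. The verdict assumes that the SAP supplied is the one to be used with Protocol version 7.

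Two stronger readings should be resisted.

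- A reader might infer a size from the Phase 2a diarrhoea rate, 18 of 44 subjects. That figure has no grade attached, pools 10 single-dose with 34 multiple-dose subjects, and covers more than a dose-adjustment period. No source gives the share of subjects peaking at 4 to 6 episodes.
- A reader might infer that subjects in both cohorts were dosed under one threshold and counted under another. The first cohort was treated under protocol versions not available here, so the discrepancy between dosing rule and table is shown only for version 7.

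**What to change.** Before any unblinding of the 1:1 cohort:

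1. Set the recurrent-diarrhoea DLT in SAP 2.6.6 and in Protocol 8.3 to 7 or more episodes within 24 hours of a dose. This matches Protocol 3.1 and is consistent with the Grade 3 cut in the 8.2 table.
2. State that the rule of 4 or more episodes on two consecutive days in Protocol 4.2 is a dose-reduction trigger and not a DLT.
3. Add to the SAP 4.8.10 table a descriptive row for subjects whose worst 24 hours had 4 to 6 episodes, not labelled DLT. Both counts are then visible, and the choice of threshold cannot hide events.
4. If the first cohort was dosed under a different DLT threshold, say so and present the diarrhoea rows by cohort.

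The cost is a corrected definition in each document, one clarifying sentence and one additional table row. Visits, dosing and sample size do not change.

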3. SUBJECT POPULATIONS

3.1. Population Definitions

The following subject populations will be evaluated and used for presentation and analysis of the data:

- **Safety Population:** The Safety Population will consist of all subjects who receive at least one dose of study medication during the study. Subjects will be analyzed based on the treatment that they actually received. All safety analyses will be based on this population.
- **Modified ITT Population:** The modified Intent-to-Treat (mITT) Population will include subjects who are randomized and have the stool diary assessments both at baseline and at least one post baseline time-point. Subjects who are found later to have inclusion/exclusion violations will be excluded from the mITT population.
- **Fixed Dose Population:** The Fixed Dose Population will include all subjects who are in mITT Population who enter the Fixed Dose period of the study and are in the treatment period for at least seven days, not including the date of randomization.
- **Efficacy Evaluable Population:** The Efficacy Evaluable Population will include subjects who are in the Fixed Dose Population, complete the Fixed Dose period, are compliant with study medication in the Fixed Dose period, and have no major protocol deviations.
- **Pharmacokinetics Population:** Pharmacokinetics Population will include subjects with a least one L-Dopa PK result.

The precise reasons for excluding subjects from the Efficacy Evaluable Population will be fully defined and documented prior to the unblinded interim analysis.

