5.3 Inclusion Criteria

The study population is defined as subjects who meet the following criteria:

1. Subjects aged 30-90 years, both genders
2. Subjects must provide written informed consent and be willing and able to comply with study procedures.
3. Subjects must be diagnosed with Parkinson's Disease defined as the presence of at least three of the following cardinal features, in the absence of alternative explanations or atypical features: rest tremor, rigidity, bradykinesia and/or akinesia, postural and gait abnormalities.
4. There are insufficient criteria for Irritable Bowel Syndrome (IBS)

5. Constipation which has been present for approximately 6 months
6. Body mass index (BMI) of 18-40 kg/m²
7. Subjects must fulfill Rome IV criteria for functional constipation which includes 2 or more of the following:
 - a. Straining during at least 25% of defecations
 - b. Lumpy or hard stools in at least 25% of defecations
 - c. Sensation of incomplete evacuation for at least 25% of defecations
 - d. Sensation of anorectal obstruction/blockage for at least 25% of defecations
 - e. Manual maneuvers to facilitate at least 25% of defecations (e.g., digital evacuation, support of the pelvic floor)
8. Self-report of 3 or fewer complete spontaneous bowel movements (CSBMs) per week
9. Loose stools are rarely present without the use of laxatives
10. Subjects must be able to read, understand, and accurately record data into the diary to guarantee full participation in the study.
11. Female subjects must have negative serum or urine pregnancy tests and must not be lactating. For females able to bear children, hormonal (i.e., oral, implantable, or injectable), abstinence, same sex relationships, single-barrier method, or a double-barrier method of birth control must be used throughout the study. A vasectomized partner will be allowed as one in conjunction with another single-barrier method.
12. Female subjects unable to bear children must have this documented in the CRF (i.e., tubal ligation, hysterectomy, or postmenopausal [defined as a minimum of one year since the last menstrual period]). Post-menopausal status will be confirmed by follicle stimulating hormone (FSH) in women less than 60 years of age

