5.4 Exclusion Criteria

1. Unable or unwilling to provide informed consent or to comply with study procedures.
2. Diagnosis of secondary constipation beyond that of Parkinson's Disease

3. Review of Screening Diaries indicates either of the following:

- Fewer than 11 days of diary completion and/or
- More than 3 complete spontaneous bowel movements per week based upon the average CSBM rate reported during the Screening Period.

4. A compromised gastrointestinal system which includes:

- Structural, metabolic, or functional GI diseases or disorders
- Acute GI illness within 2 weeks of the screening visit
- History of major GI surgery within 30 days of the screening visit (a history of cholecystectomy, polypectomy, hernia repair or appendectomy are not exclusionary as long as they were performed more than 30 days before the screening visit)

5. Unable or unwilling to withdraw from laxatives, opiates, clonazepam, or any medications which may cause constipation, 2 weeks prior to the dose adjustment period and throughout the rest of the study.

6. Unable or unwilling to withdraw from proton pump inhibitors and antacids at the end of the screening period.

7. Any clinically significant abnormalities on screening laboratories or physical examination requiring further evaluation or treatment.

8. Neurological disorder other than Parkinson's Disease that in the opinion of the investigator might interfere with the conduct of the study.

9. On treatment with intra-jejunal dopamine or carbidopa/levodopa (i.e. Duopa).

10. Subjects starting a new Parkinson's Disease medication or modifying an existing medication within 2 weeks prior to enrollment.

11. Unable to maintain a stable diet regimen.

12. Subjects with a cognitive impairment that preclude them from understanding the informed consent.

13. Subjects placed under legal guardianship.

14. Females who are pregnant or breastfeeding.
15. History of excessive alcohol use or substance abuse.
16. Participation in an investigational drug trial within the month prior to dosing in the present study.
17. Any other reason, which, in the opinion of the investigator, would confound proper interpretation of the study.

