9 DATA MANAGEMENT AND STATISTICS

9.0 Populations for Analyses

The following populations will be considered for statistical analyses.

- **Safety Population:** The Safety Population will consist of all subjects who receive at least one dose of study medication during the study.
- **Modified ITT Population:** The modified Intent-to-Treat (mITT) Population will include subjects who are randomized and have the stool diary assessments both at baseline and at least one post baseline time-point.
- **Fixed Dose Population:** The Fixed Dose Population will include all subjects who are in mITT Population who enter the Fixed Dose period of the study.
- **Efficacy Evaluable Population:** The Efficacy Evaluable Population will include subjects who are in the Fixed Dose Population, complete the Fixed Dose period, are compliant with study medication in the Fixed Dose period, and have no major protocol deviations.

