4.6. Efficacy Analyses

Efficacy analyses to evaluate the treatment effect will be conducted using the Fixed Dose population as the primary population. The analyses will also be performed using the mITT and Efficacy Evaluable populations. Summary statistics will also be presented.

The comparison of active versus placebo treatment will be tested at the two-sided 0.05 significance level.

The date of randomization will not be included for either baseline or post-baseline weekly efficacy endpoints (i.e., rates or mean values). Similarly, the date of the single-blind period visit will also not be used in derivation of weekly efficacy endpoints (rates or mean values). Also, the visit 5 Date (ie, the date the patient begins the Washout period) will be included in the single-blind period (i.e., the single-blind period lasts from the day after Visit 4 up to and including Visit 5).

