5. CHANGES TO PLANNED ANALYSES

As of this date, there have been no changes between the protocol-defined statistical analyses and those presented in this statistical plan.

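### SAP 3.1 drops randomized subjects with later-discovered eligibility violations from mITT, and so from every efficacy analysis, with no pre-randomization or blinding limit and contrary to Protocol 9.0

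*SAP*

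**What the plan says.** Protocol 9.0 and the protocol synopsis define mITT by randomization and diary data alone: "The modified Intent-to-Treat (mITT) Population will include subjects who are randomized" and have a diary assessment at baseline and at least one afterwards. SAP 3.1 repeats that definition and then adds: "Subjects who are found later to have inclusion/exclusion violations will be excluded from the mITT population". SAP 5 nevertheless states that "there have been no changes between the protocol-defined statistical analyses and those presented in this statistical plan".

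The other two efficacy populations in SAP 3.1 are built on mITT:

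- "The Fixed Dose Population will include all subjects who are in mITT Population who enter the Fixed Dose period of the study" (with at least seven days in the treatment period).
- "The Efficacy Evaluable Population will include subjects who are in the Fixed Dose Population, complete the Fixed Dose period", with further compliance and deviation conditions.

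SAP 4.6 makes Fixed Dose the primary population and adds: "The analyses will also be performed using the mITT and Efficacy Evaluable populations". No other efficacy population is defined. SAP 4.6.3 declares success on the Fixed Dose ANCOVA at p<0.05.

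SAP 3.2 describes a violation file finalised before database lock, but it decides exclusion from Efficacy Evaluable only. The undertaking in SAP 3.1 to document exclusion reasons before the unblinded interim analysis is limited to the same population.

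**The concern.** An eligibility exclusion from mITT is usually defensible only when it turns on facts settled before randomization and is decided without knowledge of treatment. The SAP sentence sets neither condition. It is mandatory, has no cut-off date and sits outside the SAP 3.2 review. Protocol 9.2.6 records that an unblinded interim analysis has already been done, and SAP 4.3 plans another once the last subject completes the Fixed Dose period.

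Some criteria are worded to continue past randomization. Exclusion 5 covers withdrawal from laxatives, opiates and constipating drugs "2 weeks prior to the dose adjustment period and throughout the rest of the study". Inclusion 11 says that contraception such as a "double-barrier method of birth control must be used throughout the study". Whether a subject returns to a laxative plausibly depends on whether the constipation was relieved. If such conduct were classed as an eligibility violation, membership of mITT would depend on the outcome, and the success test would no longer compare the groups as randomized.

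**Working it through.** **Step 1. How far a removal reaches.** By definition, Efficacy Evaluable ⊂ Fixed Dose ⊂ mITT. These are the only efficacy populations, so one removal from mITT takes the subject out of the success test and both of the other population analyses. The Safety and Pharmacokinetics populations are unaffected.

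**Step 2. What can count as a violation.**

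| Points to entry facts only | Leaves room for on-treatment facts |
|---|---|
| The schedule of events checks eligibility at Visits 1 and 2 only | Exclusion 5 runs for the rest of the study |
| A committee rules on eligibility before randomization (Protocol 4.1, 4.2, 8.14) | Inclusion 11 runs throughout the study |
| Protocol 5.7 leaves bowel movements within 24 hours of on-study laxative use uncounted and does not call for removing the subject | SAP 3.1 has no pre-randomization limit |

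The left column is the more natural reading. Nothing in SAP 3.1 makes it the only one.

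**Step 3. Possible size.** The plan gives no figure for this rule and no removal rate, so this is an illustration on assumed values.

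*Analysis set (assumed).* SAP 4.1 anticipates 64 evaluable subjects in part 1; at 3:1 that is 48:16. With difference 2.4 − 0.5 = 1.9, SD 2.0 and a two-sided 0.05 t-test, the noncentral t gives power 0.900, which matches the SAP's 90%. Part 2 is 80 less 10% drop-out (Protocol 9.2.5) = 72, or 36:36. The total is 84:52.

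*Standard error.* With the protocol's SD of 3.88: SE = 3.88 × √(1/84 + 1/52) = 0.685.

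*Shift in one arm.* If a fraction p is removed, the arm mean is m and the removed subjects average r, then shift = p(m − r)/(1 − p).

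- Floor: exclusion 3 bars a screening average above 3 CSBM/week, and a rate cannot be negative, so r cannot be below −3. The planning means are 1.28 and 3.55 (Protocol 9.2.5).
- p = 5%, m = 1.28: 0.05 × 4.28/0.95 = 0.23.
- p = 5%, m = 3.55: 0.05 × 6.55/0.95 = 0.34.
- Random removal from the lower half of a normal distribution: m − r = 0.798 × 3.88 = 3.10, so the shift is 0.05 × 3.10/0.95 = 0.16.

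*Two-sided error under the null with bias b* = Φ(−1.96 + b/SE) + Φ(−1.96 − b/SE).

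| Case (5% of one arm) | b | Share of the planned 2.27 difference | b/SE | Error |
|---|---|---|---|---|
| Lower half, random | 0.16 | 7% | 0.24 | 5.6% |
| Floor, mean 1.28 | 0.23 | 10% | 0.33 | 6.2% |
| Floor, mean 3.55 | 0.34 | 15% | 0.50 | 8.0% |

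*Power.* Unselective removal costs little. An ordinary pooled t-test at 84:52, with difference 3.55 − 1.28 = 2.27 and SD 3.88, has power 0.909. With 5%, 10% and 15% removed from both arms it is 0.894, 0.877 and 0.858. The issue is selection, not sample size.

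**The case against.** The strongest reply is that the sentence means what such sentences usually mean: a subject was ineligible at entry and this came to light afterwards. The eligibility schedule, the pre-randomization committee and Protocol 5.7 all fit that reading, and no passage says that resumed laxatives will be coded as an eligibility violation. A reader might infer that several criteria can be judged only after randomization. The documents do not support that: screening is run off laxatives, and the diary requirement is tested by the 11-day rule before randomization. This part of the reply stands. What remains is that the SAP permits the other reading; it does not prescribe it.

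Second, removals will not be hidden. SAP 4.4 summarizes population allocation by randomized treatment, and SAP 3.2 lists all protocol violations. That also stands, although counts and listings are not an efficacy estimate that keeps these subjects.

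Third, removals driven by lack of relief would be balanced under the null, and if ENT-01 works they would fall mainly on placebo and count against ENT-01. That is correct. The error rates above need removals confined to one arm, through intolerance or knowledge of assignment for example. The documents do not say who saw assignments at the completed interim analysis, so a reader should not infer that the exclusions will be chosen by people who know them.

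**Conclusion.** The point holds as an undeclared departure from the protocol's mITT definition, open-ended in time and in the facts it may use, with no blinding or pre-lock condition, and carried by nesting into every planned efficacy analysis. Dependence on outcome is possible under the wording but is not established. It should be fixed.

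The size is modest and conditional. At an assumed 5% removed from one arm, the shift is about 0.16 CSBM/week for random removal from the lower half and at most about 0.23 to 0.34, with two-sided error of about 5.6%, 6% and 8%. The rate, the one-arm restriction and the 84:52 set are assumptions, and the direction depends on the arm. The floor of −3 assumes that the removed subjects met the entry limit on screening CSBM rate.

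A reader might instead trim the worst 5% of a normal distribution with SD 3.88, which gives a shift of 0.42 and error of about 9%. Those figures are not attainable here. The trimmed subjects would have to average 8.0 CSBM/week below the arm mean (3.88 × 2.063), which is a change of −6.7 from a mean of 1.28 or −4.5 from a mean of 3.55. Both lie below the floor.

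**What to change.** Delete the added sentence from SAP 3.1 so that mITT matches Protocol 9.0. Let major violations, including eligibility violations, remove subjects only from Efficacy Evaluable, through the pre-lock file already described in SAP 3.2.

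If the sponsor wants to keep an mITT exclusion, limit it to criteria determined from pre-randomization data, have it decided blind to arm before any unblinding, and declare it in SAP 5. The entry limit would then also have to be reconciled: Protocol 4.2 requires a screening average under 3 CSBM/week, whereas exclusion 3 and the 1.0–3.0 stratum admit exactly 3.0.

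The cost is one SAP sentence. A few ineligible subjects would stay in mITT and Fixed Dose, which may slightly dilute the estimate. The Efficacy Evaluable analysis would still show the result without them.
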